## **VI. Study Procedures**

All consecutive patients with symptomatic cholelithiasis who underwent elective LC between January 2020 and June 2021 will be considered for enrolment in the study. Patients who required urgent surgery due to acute cholecystitis will be excluded. The other exclusion criteria will be age under 18 years, previous umbilical hernia repair, and pre-existing umbilical hernia.

Operations will be performed by four experienced surgeons. A supraumbilical transverse skin incision followed by an open technique with a vertical incision will be performed. Four trocars will be used. One 10-mm trocar was placed, and pneumoperitoneum will be obtained. A 30-degree endoscope will be inserted through this trocar. One 10-mm trocar (at the epigastrium) and two 5-mm trocars (at the right subcostal and lower right quadrant) were inserted under direct visualization. The gallbladder will be removed through the umbilical incision with an endo bag. The umbilical incision will be enlarged if needed to be for extraction of the gallbladder. After the extraction of the gallbladder, the size of the fascial defect will be measured directly using a ruler. The method of umbilical fascial closure for each patient will be determined using the computerized random generation of a number just before the operation. The number was given to the surgeon and the previously assigned umbilical fascial closure technique (assigned to that number) will be used. Patients will be randomly assigned to the umbilical closure non-video-assisted (UC) and umbilical closure with video-assisted (UCVA) groups.

In the UC group, the umbilicus incision will be closed with an interrupted suture with synthetic absorbable 0 suture (Pedesente®, Dögsan A.S., Trabzon, Turkey). In the UCVA group, the laparoscope will be inserted the epigastric trocar and the umbilical fascial defect will be visualized intraabdominal. Then the defect will be closed an interrupted suture with synthetic absorbable 0 suture (Pedesente®, Dögsan A.S., Trabzon, Turkey) including all layers of the abdominal wall under the direct reverse vision of the defect with a 30° laparoscopic camera.

The skin closure will be performed using a 3/0 polypropylene suture (Sterilen®, Dögsan A.S., Trabzon, Turkey). Patients' operative characteristics will be recorded after the operations.

All patients will receive standard postoperative care, including mobilization and returning to a normal diet as quickly as possible. Patient-controlled analgesia (tramadol 100 mg) will be provided for the first 24 h after surgery. A nonsteroidal anti-inflammatory agent (diclofenac 25 mg, intramuscular, two times daily) will be given until discharge from the hospital.

Visual analog scale (VAS; range 0- 10) will be evaluated one day before the surgery (VASP). Also, postoperative (PO) first day (VAS1) were recorded.

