## **III. Study Aims**

We hypothesized that the fascial closure of the umbilical trocar incision under the intraabdominal vision with the laparoscopic camera could be reduced TSH. This prospective randomized controlled study aims to assess whether fascial closure of umbilical trocar site under direct laparoscopic vision in LC can reduce the incidence of TSH.

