## **V. Study Design**

All consecutive patients with symptomatic cholelithiasis who underwent elective LC between January 2020 and June 2021 will be considered for enrolment in the study.

Patients who required urgent surgery due to acute cholecystitis will be excluded. The other exclusion criteria will be age under 18 years, previous umbilical hernia repair, and pre-existing umbilical hernia. All patients who enrolled in the trial will be provided an informed consent form

The sample size calculation was based on the data of a previous study. TSH rate was 6.6% in patients who underwent laparoscopic cholecystectomy. With a statistical power of 80% and a significance level of  $p < 0.05$ , the required sample size was 92 patients. Statistical analysis was performed using IBM SPSS Statistics version 20.0 (SPSS Inc., Chicago, IL, 2011) for Windows. Results were compared by the Student-t test or Mann-Whitney-U test for continuous variables and Chi-square or Fisher exact tests were used for categorical variables. A p-value  $< 0.05$  was considered to represent statistical significance.

The primary outcome endpoint in the study is the presence of a TSH. Secondary endpoints are operative complications, wound infection, hematoma, pain, and length of hospital stay. Patients will be evaluated by clinical examination. If the surgeon suspected a TSH, abdominal ultrasound and/or abdominal computed tomography will be carried out. Any wound hematoma will be considered as a postoperative complication when they limited daily activities or required drainage. Wound infection will be defined as the presence of pain, redness, and purulent discharge at the umbilical trocar incision.

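### The closure technique is randomised before surgery although the arms differ only at umbilical closure; randomising after the defect is measured would be a cheap, optional improvement

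*Protocol*

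**What the plan says.** The trial question in Protocol section III, Study Aims, concerns closure alone: to "assess whether fascial closure of umbilical trocar site under direct laparoscopic vision in LC can reduce the incidence of TSH". The arms in section VI, Study Procedures, match it: "Patients will be randomly assigned to the umbilical closure non-video-assisted (UC) and umbilical closure with video-assisted (UCVA) groups".

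Section VI describes the steps before closure once, for all patients. These are access, trocar placement and extraction, then:

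- discretionary enlargement: "The umbilical incision will be enlarged if needed to be for extraction of the gallbladder";
- measurement: "After the extraction of the gallbladder, the size of the fascial defect will be measured directly using a ruler".

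The allocation follows in the text: "The method of umbilical fascial closure for each patient will be determined using the computerized random generation of a number just before the operation". The next sentence covers hand-over, with no time attached: "The number was given to the surgeon and the previously assigned umbilical fascial closure technique". The first step that belongs to one arm only is in the UCVA closure: "the laparoscope will be inserted the epigastric trocar and the umbilical fascial defect will be visualized intraabdominal".

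Section V, Study Design, names the primary endpoint: "The primary outcome endpoint in the study is the presence of a TSH". Nowhere does the protocol say that the surgeon, or whoever measures the defect, is kept unaware of the arm until closure.

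**The concern.** The plan randomises earlier than the comparison requires. Two consequences follow.

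1. **Knowledge of the arm before closure is not ruled out.** The umbilical fascial defect is the wound whose hernia is the primary endpoint. Whether it is enlarged depends on need during extraction, as the operator sees it, and no criterion for need is given. If the operator already knows the technique to follow, neither the enlargement nor the measurement is protected from that knowledge. A difference in defect size between arms could then not be put down to chance with certainty.

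2. **Patients are randomised before they reach the step being compared.** This holds whenever the number is handed over. A patient in whom umbilical trocar closure is never done has been allocated to a technique that could not be applied. Keeping that patient dilutes the comparison; dropping that patient is an exclusion after randomisation. Defect size also becomes a value recorded after randomisation, not a baseline value.

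**Working it through.** **Order of events.** The protocol has no figure to reproduce here, so the check starts with the steps in section VI.

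| Step | Differs by arm? | Depends on the operator? |
|---|---|---|
| Random number generated, before surgery starts | – | – |
| Access, trocars, gallbladder extraction | No | – |
| Enlargement of the umbilical incision where needed | No | Yes |
| Ruler measurement of the fascial defect | No | Yes |
| Umbilical fascial closure, UC or UCVA | **Yes** | – |
| Number handed to the surgeon | Time not stated | – |

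Hand-over could fall anywhere from the start of surgery to closure. The hand-over sentence comes after the measurement sentence, which allows the reading that the surgeon learns the arm only at closure. But the sentence on generating the number also comes after the measurement sentence, although it describes something done before surgery. The order of sentences therefore does not settle the order of events.

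**Consequence 1 (arm known early).** The protocol gives nothing from which the size or direction of a bias could be calculated, so no figure is claimed.

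**Consequence 2 (randomised but closure not reached).** Inputs:

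- Sample size 92, from section V. The text does not say whether this is the total or per arm; if per arm, the total is 2 × 92 = 184.
- Share of patients not reaching umbilical trocar closure, f. The protocol gives none; the assumed range is 1% to 5%.

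Patients affected = N × f:

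| N | f = 1% | f = 5% |
|---|---|---|
| 92 | 92 × 0.01 = 0.92 | 92 × 0.05 = 4.6 |
| 184 | 184 × 0.01 = 1.84 | 184 × 0.05 = 9.2 |

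Effect on the comparison: let d be the risk difference among patients who reach closure. Suppose f is the same in both arms, patients who do not reach closure have the same hernia risk in both arms, and everyone is analysed as randomised. Then

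risk difference among all randomised = (1 − f) × d + f × 0 = (1 − f) × d,

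which is 0.99 d at f = 1% and 0.95 d at f = 5%.

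**Cost of randomising later.** Patients to consent = patients to randomise ÷ (1 − f). For 92 randomised:

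- f = 1%: 92 / 0.99 = 92.9, so 93
- f = 5%: 92 / 0.95 = 96.8, so 97

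**The case against.** The strongest reply is that nothing here is wrong. Generating a random number shortly before surgery is ordinary, acceptable practice, and the protocol does not contradict itself. That stands, and the point is put as an improvement, not as a flaw in the randomisation.

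Next, the first consequence rests on silence. The number may well be handed over at closure, in which case the arm was unknown during enlargement and measurement. The protocol also ties enlargement to the needs of extraction, gives no reason for it to differ by arm, and plans no use of defect size in the analysis. All of this stands and is why no bias is asserted. What remains is that the text does not secure what it may intend.

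Third, one clause withholding the number until after measurement would do. This is half right. It would deal with the first consequence, but patients who never reach closure would still be randomised. Only later generation removes both.

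Fourth, the second consequence is small, rests on an assumed share, and arises as dilution only if all randomised patients are analysed, a choice that may sit in an SAP not at hand. This is correct as to size. If such patients are excluded instead, the dilution goes, but an exclusion after randomisation takes its place.

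Finally, the protocol describes neither theatre staffing nor where the generator is used, so the low cost is a judgement. That also stands.

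**Conclusion.** The point holds as an optional improvement of low priority. The protocol fixes randomisation before surgery, leaves the hand-over time open, and compares techniques that differ only at a later step. Moving allocation to just before that step guarantees by design that the arm cannot influence the size of the defect or its measurement, and that every randomised patient has reached the closure under comparison.

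The stakes are modest. Bias from early knowledge of the arm is possible but neither shown nor quantifiable from the protocol. The gain from not randomising patients who never reach closure is at most a few patients if 92 is the total (up to 9.2 if it is per arm), and 1% to 5% of the risk difference. Those figures rest on the assumed 1% to 5% share, on that share and the hernia risk of these patients being equal between arms, and on analysis of all randomised patients.

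**What to change.** In section VI, replace the sentence on when the number is generated with wording such as:

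> The random number is generated in the operating room, by theatre staff other than the operating surgeon, only after the gallbladder has been extracted and the size of the fascial defect has been measured and written down; it is then given to the surgeon. Patients who do not reach this point are not randomised.

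Add that patients who consented but were not randomised are logged and do not count towards the 92. Defect size is then a value recorded before randomisation, and any difference between arms in it is due to chance.

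The surgical steps, power and significance level do not change. The cost is a short task during the operation: someone other than the surgeon writes down the defect size, generates the number and passes it on. That such a person is available, and that the generator can be used in theatre, are assumptions. No extra visits are needed. Consent would be sought from 93 to 97 patients for 92 randomised, under the assumed 1% to 5%.

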#### *Follow-up*

All patients will be scheduled to return for an outpatient visit in the second week and every three months after the surgery.

